5.4 PARTICIPANT WITHDRAWAL OR TERMINATION

5.4.1 REASONS FOR WITHDRAWAL OR TERMINATION

In accordance with the guiding principles of the Declaration of Helsinki, any patient is free to withdraw from participating in this study at any time and for whatever reason, specified or unspecified, and without prejudice. Investigators should attempt to determine the cause of withdrawal and, if desired by the patient, to make it possible for the patient to continue to participate in the study. The extent of a patient's withdrawal from the study (i.e. withdrawal from further study treatment, withdrawal from any further contact, etc.) should be documented. Every effort should be taken to follow all randomized patients, to the extent that the patient will allow, for the full follow-up period.

Investigators may discontinue study treatment for any other reasons concerning the health or well-being of the patient.

The reason for and date of study discontinuation and the reason for and date of withdrawal from the study must be recorded on the CRF. If study is discontinued because of an adverse event or a clinically significant abnormal laboratory test result, evaluations will continue until the event has resolved or stabilized or until a determination of a cause unrelated to the study procedure is made. The specific event or laboratory finding(s) must be documented. All evaluations should be performed, according to the protocol.

5.4.2 HANDLING OF PARTICIPANT WITHDRAWALS OR TERMINATION

The Full Analysis Set (FAS) will include all randomized patients. In accordance with the intent-to-treat principle, patients will be analyzed by the group to which they were randomized. Misrandomized patients (patients randomized in error who did not receive any study intervention) will be excluded. Analyses in the FAS will constitute the main efficacy results for the primary and secondary study efficacy endpoints.

The Per Protocol Set (PPS) will be a subset of the FAS and will exclude patients with major protocol violations. The major protocol violations that will result in exclusion from the PPS will be identified. Patients will be analyzed in the treatment group to which they were randomized. Results of analyses in this analysis population will support the primary efficacy analyses in the FAS.

5.5 PREMATURE TERMINATION OR SUSPENSION OF STUDY

The study is overseen by a DSMB. They may terminate the study at any time if the safety of patients is at jeopardy.

[figure not shown]
6 STUDY AGENT

6.1 STUDY AGENT(S) AND CONTROL DESCRIPTION

This study will test a strategy-of-care, SSU AHF management for less than 24 hours vs. usual care (hospitalization) for lower risk AHF patients who are planned to be admitted. Only therapies commonly utilized during usual AHF care will be applied. For example, , IV loop diuretics, and topical and oral vasodilators. Usual care will be at the discretion of the clinical care team. No drugs or therapies that are not approved by the FDA will be allowed.

6.1.1 TREATMENT PROTOCOL

The algorithm below outlines the SSU AHF protocol.

Arm 1. SSU AHF Strategy: 'Short stay' is defined as < 24 hours. All SSU are monitored beds. Nursing ratios are similar to telemetry wards. Four principles of SSU AHF management are outlined: 1) relief of HF symptoms and signs; 2) decongestion while observing and correcting any electrolyte imbalances; 3) hemodynamic improvement; and 4) robust care transitions with an emphasis on guideline directed medication reconciliation and guideline recommended therapy at discharge.^{16,46} One potential advantage of the SSU AHF strategy is protocol driven care. (See Figure 3, next page) This figure is adapted from the ESC and SCPC Guidelines, primarily adding greater detail regarding vasodilator and diuretic dosing.⁴⁷ "Warm and wet" defines the HF phenotype from the Nohria et.al. classification: well perfused, volume overloaded.⁴⁸ The discharge criteria are taken from the SCPC guidelines on observation unit care.¹⁶

Arm 2. Usual care (defined by inpatient admission for AHF) was chosen as the comparator. In 2009, Dawson et.al. published the background framework for the 2005 NIH funded meeting on "Considering Usual Care in Clinical Trial Design: Scientific and Ethical Issues."⁴⁹ These principles informed our decision to use 'usual care' as the comparator.

One specific principle: consideration of ‘usual care’ when a comparator hypothesizes to be better than or equivalent to current clinical practice.⁴⁹ Hospitalization is the dominant strategy of care for over 80% of patients who present to the ED with AHF; thus, it provides the best real-world comparison of AHF care.⁵⁰ The median length of stay is 4.3 days.¹ We expect nearly all usual care patients to be cared for on general wards or telemetry and not ICU level of care, given our lower risk eligibility criteria. Guidelines are clear on suggested best practices for management.⁴⁹ Admittedly, the evidence supporting these statements in AHF are not as robust as chronic HF. This is one reason usual care has frequently been used in AHF therapeutic clinical trials.⁵¹⁻⁵³ Nevertheless, we will encourage guideline adherence in BOTH arms of the trial, both during hospitalization and pre-discharge. As hospitals are penalized on excessive 30-day readmissions, each participating hospital has a transitional care plan. In keeping with the pragmatic study design, each study arm will utilize their existing transitional care programs.

6.1.2 DURATION OF THERAPY

Both arms will continue until patients are deemed ready for discharge, either from the SSU or the hospital. For patients deemed not ready for discharge after the SSU management phase, will be admitted.

7 STUDY PROCEDURES AND SCHEDULE

7.1 STUDY PROCEDURES/EVALUATIONS

7.1.1 STUDY SPECIFIC PROCEDURES

The table below in section 7.3.7 highlights study specific procedures. Only patients who sign written informed consent will undergo study specific procedures.

7.1.2 STANDARD OF CARE STUDY PROCEDURES

There will be no other change to standard of care procedures for either treatment arm. Patient care and safety are paramount and trump all other considerations.

7.2 LABORATORY PROCEDURES/EVALUATIONS

7.2.1 CLINICAL LABORATORY EVALUATIONS

Lab testing will be based on standard practice and likely include analyzed by the clinical lab at each respective institution for baseline chemistry and hemoglobin/hematocrit values. This reflects our pragmatic approach. Only labs collected as part of usual or standard care will be collected. No lab testing will be done solely for research purposes.

If drawn, all clinical laboratory test results outside of the reference range will be interpreted in the context of the patient underlying disease state by the Investigator using the following categories:

- abnormal but not a clinically-significant worsening
- abnormal and a clinically-significant worsening

A local laboratory will be utilized to analyze screening entry criteria. Laboratory tests not specified in the protocol but required by the Investigator to assess patient care will be performed at the local laboratory in accordance with Standard of Care.

7.3 STUDY SCHEDULE

7.3.1 SCREENING

A signed and dated informed consent form will be obtained before any study-specific screening procedures are performed. Results of evaluations obtained as part of routine medical care, which are performed prior to obtaining

informed consent, may be used in place of the protocol-specified evaluations. Patients will acknowledge and agree to the use of this information for the study by giving informed consent.

At the Baseline Visit, patients will be assigned by the IWRS a unique permanent identification number (referred to as the patient identification number) such that all randomized patients from each center are given consecutive identification numbers by the IWRS in successive order of inclusion. We will utilize the REDCap randomization module.

Prospective study patients will have presented to the hospital for urgent therapy for AHF. Potential patients will be identified either en route to or upon arriving at the ED/hospital. Routine assessments associated with usual patient care may be used for the purposes of screening and may be completed in any order. Study specific procedures must be completed only after Informed Consent is obtained.

Randomization will occur during the patients ED stay. This may occur at any time during their ED stay.

The following procedures will be performed prior to or during Screening:

- Obtain written informed consent (must be performed as the first study-specific procedure)
- Review and record medical history
- Record prior and concomitant medications
- Physical examination (including height and weight when reasonably possible)
- Vital signs measurements (includes systolic and diastolic blood pressures, heart rate, body temperature, oxygen saturation reading and respiratory rate)
- 12-Lead Electrocardiogram per standard practice
- Blood collection for local laboratory tests, including BNP or NT-proBNP, and pregnancy test if applicable per local standard practice.
- Inquiry about Adverse events

7.3.2 ENROLLMENT/BASELINE

Patients who continue to fulfill all of the inclusion/exclusion criteria will be randomized. Randomization will occur via central IWRS system.

7.3.3 FOLLOW-UP & FINAL STUDY VISIT

Patients will have follow up at 30 (+/- 7 days) days and 90 (+/- 30) days post-discharge (up to 120 total days after randomization is allowed if difficult to get a hold of a patient or more time is required to complete forms). There will be NO further in-person visits once discharged. However, treatment during hospitalization will be recorded. Patients will be called 30 days post-discharge ((+) 7 business days) and 90 days post-discharge (+/- 30 days) to assess vital status, re-hospitalizations or ED visits, as well as quality of life, caregiver burden, and resource utilization.

7.3.7 SCHEDULE OF EVENTS TABLE

Schedule of Events Timepoint/Visit	Screen	Baseline	ARM 1 - PreDischarge from SSU	ARM 2 - PreDischarge from Hospital Floor	30-Day & 90 Day Follow up
Informed Consent	X				
Medical History		X			
Physical Exam		X	X	X	
Clinical lab tests*		X	X~	X~	
ECG*		X			
CXR*		X			
KCCQ (QoL) & SF-12			X	X	X
Oberst Caregiving Burden Scale and Bakas Caregiving Outcomes Scale			X	X	X ¹
HF Guideline Assessment			X	X	
Collect concomitant meds		X	X	X	
mRUQ-HF (resource utilization)					X ²
Cost Effectiveness Measures (i.e. DRG)					X
Guideline adherence assessment		X	X	X	X ¹
SCPC Discharge Criteria Adherence			X	X	
Assessment of AE/SAE's through 5 days			X	X	
Vital Status, ED visits, Hospital days, Re-admission status			X	X	X
Subject Payment			X	X	X ²

*per standard of care. Typical labs include: Na, K, renal function, HgB, troponin, Natriuretic Peptide levels. ~only if performed per usual care

SOC = standard of care, ED = Emergency Department, QoL = quality of life, HF = heart failure, mRUQ = modified resource utilization questionnaire, EMR = electronic medical record, DRG = diagnosis related group

¹Only through 30 days

²Sites may choose to make a single payment or to divide into 2 payments.

³only at 90 days

NOTE: If patients are hospitalized from the SSU, ONLY the following assessments should be collected. Otherwise, the pre-discharge assessments will apply.

- Physical exam
- Clinical lab tests
- Con meds
- SCPC discharge criteria. This would be conducted twice. Once in SCPS prior to hospitalization and again at discharge.

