8.1.1 DEFINITION OF ADVERSE EVENTS (AE)

The Investigator and study staff are responsible for detecting and recording AEs and SAEs during scheduled safety evaluations and whenever such information is brought to their attention. This section of the protocol provides definitions and detailed procedures to be followed. During each visit, the Investigator will question the patient about adverse events using an open question, taking care not to influence the patient's answers, e.g. "Have you had any unusual symptoms or medical problems since the last visit? If yes, please describe."

An AE is any unfavorable and unintended sign, symptom, or disease temporally associated with the use of an investigational (medicinal) product or other protocol-imposed intervention, regardless of attribution. It is expected that many HF patients will have events that are commonplace due to their HF and associated comorbidities. Our study plans to focus on AE that are outside of what is typically encountered during an AHF event and the subsequent 90 days.

This includes the following:

- AEs not previously observed in the subject that emerge during the protocol-specified AE reporting period (5 days for anything other than mortality, re-hospitalization, and ED visits)
- Complications that occur as a result of protocol-mandated interventions such as a medication adjustment
- Preexisting medical conditions (other than the condition being studied) judged by the investigator to have worsened in severity or frequency or changed in character during the protocol-specified AE reporting period that are outside of what would be expected for a patient with AHF or HF in the outpatient setting.

For example, a patient upgraded to ICU status from the observation or SSU. Hospitalization, by itself, does NOT count as it is expected to occur for a proportion of SSU patients.

- Abnormal laboratory values that fall into an abnormal range based upon the hospital's laboratory standards, the abnormality was not preexisting prior to enrollment, and the abnormality leads to a new treatment within the AE time frame, with the exception of repleting potassium.

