8.1.2 DEFINITION OF SERIOUS ADVERSE EVENTS (SAE)

An AE will be classified as an SAE if:

- It results in death (i.e., the AE actually causes or leads to death).
- It is life threatening (i.e., the AE, in the view of the investigator, places the subject at immediate risk of death. It does not include an AE that, had it occurred in a more severe form, might have caused death).
- It requires or prolongs inpatient hospitalization. Admission from the SSU itself does not count as an SAE, but an expected outcome. However, if in the investigators judgment, admission from the SSU was due to some other complication of the study protocol, rather than an expected outcome, it should be reported as an SAE

SPECIFIC REPORTABLE SAE for SSU/OU arm patients:

- Cardiac arrest

- Need for intubation or positive pressure ventilation
- It results in persistent or significant disability/incapacity (i.e., the AE results in substantial disruption of the subject's ability to conduct normal life functions).
- It is considered a significant medical event by the investigator based on medical judgment (e.g., may jeopardize the subject or may require medical/surgical intervention to prevent one of the outcomes listed above).

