8.4 REPORTING PROCEDURES

8.4.1 ADVERSE EVENT REPORTING

The study period during which AEs must be reported begins after informed consent is obtained and initiation of study treatment and for 5 days after randomization. Patients will be followed out to 90 days for death, ED utilization, and re-hospitalization as part of the study outcomes, which will also count as safety measures. Subject's hospital discharge summaries will be examined at hospital discharge and all non-exempt AEs will be investigated by examining necessary medical records.

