10.4.2 ANALYSIS OF THE PRIMARY EFFICACY ENDPOINT(S)

Patient baseline characteristics will be tabulated for both SSU and usual care groups. Specifically, means (standard deviations) or medians (interquartile range) will be presented for continuous variables such as age and body mass index. For categorical variables, such as gender and race, frequency and percentages will be presented. Group comparisons of continuous variables will be based on either two-sample t-tests (under normality) or Wilcoxon's Rank Sum test. Normality of distribution will be determined using the Kolmogorov-Smirnov goodness-of-fit test. Categorical data comparisons will be presented based on the Chi-square or Fisher's exact test. Standardized difference is used to compare the mean of the SSU and usual care groups.⁷²

In-hospital and SSU measurements: Data points collected during hospitalization and the SSU (e.g. medications, therapy, changes in renal function, and discharge medications) will be compared between the SSU and usual care groups using the same methods as for baseline variables. A two-sided p -value less or equal to 0.05 is considered statistically significant (without multiplicity adjustment).

Comparison on DAOOH (primary outcome): The DAOOH will be compared between the two arms using two-sample t-test. Statistical significance will be declared at 5% level (two-sided). We will also fit a linear regression model, which includes the intervention arm indicator and the site variable (e.g. a categorical variable with four levels) as the covariates. The regression model will account for variation among sites so that the power in detecting intervention effect can be improved. It will also allow us to assess potential heterogeneity in intervention effect among sites through testing the interaction between the two covariates.

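### The plan sets a 5-day adverse event window in both arms but schedules AE/SAE assessment only before discharge, so events that lead to no ED visit or readmission are not ascertained comparably

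*Combined protocol and SAP*

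**What the plan says.** Section 8.4.1 starts AE reporting at consent and start of study treatment and runs it "and for 5 days after randomization", with no distinction by arm. Section 8.1.1 gives the same period: "5 days for anything other than mortality, re-hospitalization, and ED visits".

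The procedures that would fill this window are these:
- **Schedule of Events (7.3.7).** The row "Assessment of AE/SAE's through 5 days" is ticked in the two pre-discharge columns and is blank in the 30/90-day column. A note on patients hospitalized from the SSU lists the only assessments to collect, and AE/SAE is not among them.
- **Follow-up (7.3.3).** "There will be NO further in-person visits once discharged". The calls cover vital status, re-hospitalizations, ED visits, quality of life, caregiver burden and resource use.
- **Record review (8.4.1).** Discharge summaries are examined at discharge, and non-exempt AEs are then investigated.
- **Passive reporting (8.1.1).** Staff also record events "whenever such information is brought to their attention".
- **SAE follow-up (8.4.2).** SAEs are followed through day 30, with no added contact.

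Section 8.1.2 has a sub-list headed "SPECIFIC REPORTABLE SAE for SSU/OU arm patients", which names cardiac arrest and intubation or positive-pressure ventilation. Section 8.2.3 exempts mechanical ventilation, invasive or not, from regulatory reporting and states no arm. Section 10.4.4 says AEs and SAEs will be reported and describes no allowance for observation time.

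**The concern.** The intervention itself decides how long a patient is in hospital, and the scheduled AE process operates only while the patient is in hospital. An SSU stay is under 24 hours (6.1.1), while the usual-care median is 4.3 days (6.1.1). If staff follow the schedule as written, most of the 5-day window goes unobserved for a patient discharged from the SSU, while most of it is observed in usual care.

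Section 2.3.1 names premature discharge as a risk of the trial. The days just after leaving are those in which milder harm from early discharge would appear. Under section 10.4.7 the DSMB may recommend early halting only for safety, and SAEs reach it through this process (8.4.2). The trial is unblinded (10.6.1) and has no events committee (10.4.5). A difference in AE counts could therefore come from ascertainment alone.

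The SSU-only sub-list adds a second asymmetry. The same event may be handled differently by arm, and the ventilation exemption in 8.2.3 conflicts with naming ventilation as reportable in 8.1.2.

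**Working it through.** The plan gives no figure for AE coverage, so there is none to reproduce. The quantity checked is the share of the 5-day window under scheduled observation, E[min(stay, 5)] / 5.

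**Inputs from the documents**
- SSU stay: under 24 hours (6.1.1), taken as 1 day.
- Usual-care stay: median 4.3 days (6.1.1), mean 5 days (10.5).
- Admitted from the SSU: 40% (10.5, described there as conservative).
- Earlier risk-matched comparison: median 25.7 hours SSU, 58.5 hours inpatient (2.2).

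**Assumptions.** Stay is lognormal and counted from randomization, and ED time between randomization and the unit is ignored.

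**Usual care**
- σ = √(2 ln(5/4.3)) = 0.549; k = ln(5/4.3)/σ = 0.275.
- E[min(L,5)] = 5·Φ(k−σ) + 5·(1−Φ(k)) = 5 × 0.392 + 5 × 0.392 = 3.92 days.
- Share: 3.92/5 = 78%. At the median stay it is 4.3/5 = 86%.

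**SSU patient discharged from the unit:** at most about 1/5 = 20%.

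**SSU arm.** Mean observed time = (1−a) × 1 + a × x, where a is the fraction admitted and x is the observed time of admitted patients, with AE assessment continuing to hospital discharge.

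| a | x (days) | Mean (days) | Share | Ratio to 3.92 |
|---|---|---|---|---|
| 0 | – | 1.00 | 20% | 0.26 |
| 0.4 | 3.92 (total stay as in usual care) | 2.17 | 43% | 0.55 |
| 0.4 | 4.45 (1 day plus a usual-care stay, capped at 5) | 2.38 | 48% | 0.61 |
| 0.4 | 5 (whole window) | 2.60 | 52% | 0.66 |

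If the note in 7.3.7 is read literally and AE assessment stops at transfer, the arm stays at about 20% (ratio 0.26) whatever the admission rate.

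**Shorter usual-care stay.** Take the median as 58.5/24 = 2.44 days with the same σ.
- Mean = 2.44 × 5/4.3 = 2.83; k = ln(5/2.44)/0.549 = 1.31.
- E[min(L,5)] = 2.83 × 0.776 + 5 × 0.095 = 2.68 days (54%).
- With 40% admitted for 1 day plus such a stay (x = 3.54): 0.6 + 0.4 × 3.54 = 2.02; ratio 2.02/2.68 = 0.75.
- With 40% admitted for 1 day plus the longer 4.3-day-median stay (x = 4.45): ratio 2.38/2.68 = 0.89.
- The extremes for x (2.69 and 5 days) give 0.63 and 0.97. With none admitted, the ratio is 1/2.68 = 0.37.
- The two medians alone give 25.7/58.5 = 0.44.

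The SSU arm is observed for less of the window in every scenario tried.

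**Illustration.** Assume a true 5-day AE risk of 10% in both arms, a constant rate and nothing captured after discharge. With the 4.3-day median, usual care would show 7.9%. The SSU arm would show 4.8% (40% admitted, 1 day plus a usual-care stay) or 2.1% (none admitted).

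**The case against.** The strongest reply is that the documents do not limit AEs to the stay. The window is 5 days in both arms, the schedule row itself says so, passive reporting is required, and SAEs are followed to day 30. This stands against inferring that the plan deliberately stops at discharge. What remains is a mismatch between the window and the procedures, because none of these provisions adds a scheduled contact after discharge.

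Second, serious harm after discharge would usually appear as death, an ED visit or readmission. These are collected in both arms to 90 days and count as safety measures (8.1, 8.4.1). This also stands, so a reader should not infer that the whole safety comparison is biased. The blind spot is the remaining non-fatal events in days 0–5.

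Third, a reader might infer that the SSU arm will look safer. The documents do not support a net direction. Shorter observation lowers SSU counts, while the SSU-only sub-list may raise them. The list does not shorten observation, and most events on it would meet the general SAE criteria of 8.1.2 in either arm.

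Fourth, no single percentage deficit in AEs can be defended. The ratio depends on the admission rate and the usual-care stay, and AEs clustered early would narrow the gap. The 4.4 days in section 2.2 is time over 30 days of follow-up and cannot serve as an index stay. Section 10.4.4 also specifies no between-arm test of AEs.

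Finally, section 10.4.2 compares "Data points collected during hospitalization and the SSU (e.g. medications, therapy, changes in renal function, and discharge medications") between arms over unequal stays, which might suggest requiring renal values at 24 hours. Labs are drawn only as part of usual care (7.2.1), so such values may not exist. That change is not proposed.

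**Conclusion.** The point holds in a limited form. Following the plan as written, non-fatal AEs and SAEs in days 0–5 that lead to neither an ED visit nor re-hospitalization are not ascertained comparably. Scheduled observation covers at most about 20% of the window for patients discharged from the SSU and about 78% in usual care. At arm level the ratio is about 0.26 with no admissions and 0.55–0.66 with 40% admitted, and perhaps 0.75–0.9 with 40% admitted if usual-care stays are as short as in the risk-matched group.

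These figures rest on the lognormal shape, the 1-day SSU stay and AE assessment continuing after transfer. The size is uncertain, but shorter SSU observation is not in doubt. The SSU-only SAE list and the ventilation exemption are a separate inconsistency. The net direction of bias is not established, and the 90-day death, ED and re-hospitalization outcomes are untouched. The point should be addressed, but it does not threaten the primary endpoint.

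**What to change.** 1. Ascertain AEs and SAEs for days 0–5 after randomization in every patient, whatever the discharge date. Use a health-record review of that window plus one dated question at the scheduled 30-day call.
2. Apply one named-SAE list to both arms.
3. Reconcile 7.3.7 (including the note that omits AE/SAE for patients hospitalized from the SSU), 8.1.1, 8.1.2, 8.2.3 (ventilation exempt, no arm stated), 8.4.1 and 8.4.2 (day 30 against 5 days).

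The cost is schedule and CRF wording, one question at an existing call, and some chart review. The downside is recall error at day 30 for events in the first 5 days, which the record review partly offsets.
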